## Sample Size and Accrual

The sample size for this emergent study will be 5 patients admitted with laboratory proven COVID-19 and pulmonary compromise. This number will be sufficient to demonstrate the safety, feasibility and possible efficacy of the GO2 PEEP MOUTHPIECE in improving oxygenation.

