## **Study Objective**

The objective of this study is to determine the safety, feasibility and efficacy of a bidirectional oxygenation PEEP mouthpiece in COVID-19 patients requiring supplemental oxygen.

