### **Deliverables and Timing**

This would serve as a limited safety and feasibility study to determine if further investigation is necessary. We estimate evaluation in 5 patients could be reached within one week. Thereafter, a more formal analysis could be performed as necessary.

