### **Research Design and Methods**

#### *Design*

This study will utilize a single center, single arm, pilot study design.

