### **Study Endpoints**

#### *Primary Endpoint*

Improved oxygen saturation by pulse oximetry after treatment with the GO2 PEEP MOUTHPIECE.

The secondary endpoints include:

1. Respiratory rate
2. Heart rate
3. Blood pressure
4. Subjective work of breathing
5. Arterial blood gases (if available)

Both primary and secondary endpoints will be used to evaluate the safety as well as the efficacy of the GO2 PEEP MOUTHPIECE.

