### **Study Procedures**

After an eligible COVID-19 patient on supplemental oxygen has been identified, the research coordinator will contact patient via HIPPA compliant communication technology. The study will be verbally explained in detail with the patient. At time of verbal consent, instruction on use of the device will be performed by research team. If the patient progresses to meet the inclusion criteria and is enrolled in the trial, baseline metrics as above will be recorded. Patients will be provided a GO2 mouthpiece to be used in conjunction with and oxygen delivery face mask set to deliver an equivalent FIO2 to their previous therapy. **All patients will be instructed to breathe slowly and deeply through the mouthpiece for 15 minutes total.** Metrics for primary and secondary endpoints will be recorded before and after use of the mouthpiece (immediately prior to use and then at 5, 10 and 15 minutes of use and then 15 minutes after cessation of use).

Any decline in patient condition will result in immediate removal of the GO2 PEEP MOUTHPIECE and further appropriate care by the critical care team.

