## Schedule of Assessments

Study Procedures	Prior to treatment with the mouthpiece	5 mins after PEEP therapy	10 mins after PEEP therapy	15 mins after PEEP therapy	15 minutes of after cessation of PEEP therapy
Consent	X				
Oxygen saturation	X	X	X	X	X
Respiratory rate	X	X	X	X	X
Heart rate	X	X	X	X	X
Blood pressure	X	X	X	X	X
Work of breathing 	X	X	X	X	X
Arterial blood gases (if available)	X			X	
Adverse events	X	X	X	X	X

 presence of any of the following: stridor, grunting, nasal flaring, or accessory muscle use

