## Statistical Analysis Plan

As an emergent COVID-19 study, our goal is to examine the safety, feasibility and efficacy of adding the GO2 PEEP MOUTHPIECE to COVID-19 patients already on oxygen therapy.

We will assess safety, feasibility and efficacy by observation of changes in the primary and secondary endpoints. At the conclusion of the study, we will assess metrics before and after application of the GO2 PEEP MOUTHPIECE, but given the few number of patients and low power of this initial study, statistical significance is not the focus of the analysis. However, we plan to provide statistical summaries that would be useful in a possible subsequent study, such as overall efficacy of the device and patterns and trends in primary and secondary endpoints.

Summary statistics on oxygen saturation (primary endpoint) and respiratory rate, heart rate, blood pressure, subjective work of breathing, and arterial blood gases as available (secondary endpoints) will be reported at each measurement occasion for each patient.

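### Five patients are said to be enough to demonstrate safety and feasibility, which a single-arm pilot of five cannot do, and the SAP judges feasibility without counting who completed or tolerated the session

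*Combined protocol and SAP*

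**What the plan says.** The Sample Size and Accrual section sets the sample at five patients and justifies it in one sentence: "This number will be sufficient to demonstrate the safety, feasibility and possible efficacy of the GO2 PEEP MOUTHPIECE in improving oxygenation".

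Other sections are more cautious. Deliverables and Timing says: "This would serve as a limited safety and feasibility study to determine if further investigation is necessary". The Design section says: "This study will utilize a single center, single arm, pilot study design". The Statistical Analysis Plan sets out to examine safety, feasibility and efficacy, acknowledges few patients and low power, and does not focus on significance. The Data Safety Monitoring Plan calls the trial very small.

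On how feasibility is judged, the Statistical Analysis Plan says: "We will assess safety, feasibility and efficacy by observation of changes in the primary and secondary endpoints". Those endpoints are oxygen saturation, respiratory rate, heart rate, blood pressure, work of breathing and, where available, arterial blood gases. The Study Endpoints section gives them a narrower role: "Both primary and secondary endpoints will be used to evaluate the safety as well as the efficacy of the GO2 PEEP MOUTHPIECE". Feasibility is not mentioned there.

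Tolerance appears elsewhere. Inability to tolerate the mouthpiece is one of the listed adverse events. The Schedule of Assessments has an adverse-events row marked at all five occasions. The Data Safety Monitoring Plan calls for the physician to document intolerance. Study Procedures foresees early removal: "Any decline in patient condition will result in immediate removal of the GO2 PEEP MOUTHPIECE".

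**The concern.** There are two linked problems.

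First, the sentence that states what the sample can deliver promises more than the design can give. The word 'possible' qualifies efficacy only. As written, five uneventful 15-minute sessions without a control group could be reported as having demonstrated safety and feasibility, and the protocol would appear to support that.

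Second, feasibility is one of three stated aims, yet the SAP reads it from vital signs and blood gases. A patient's saturation may rise or fall whether or not the device was used for the full session. The aim could therefore be reported without saying how many patients finished. For a pilot meant to inform a possible later study, that count is among the most useful things it can provide.

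**Working it through.** **1. Can the figure of five be reproduced?** No. The documents give no significance level, power, effect size, event rate, precision target or success threshold. The number is therefore neither derivable nor refutable; only the claim attached to it can be checked.

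**2. What five patients can show about an event.** Inputs: n = 5, single arm (Sample Size and Accrual; Design). Assumption: 95% confidence, since the plan states no level. The event must be one that is decided yes or no for each patient.

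If no patient has the event, the exact upper limit is 1 − a^(1/n):

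- two-sided, a = 0.025: 1 − 0.025^(1/5) = 0.522, so up to 52%
- one-sided, a = 0.05: 1 − 0.05^(1/5) = 0.451, so up to 45%

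The chance of seeing no event in five patients is (1 − p)^5. The true rates p are assumed for illustration:

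| True rate | Chance of 0 of 5 |
|---|---|
| 10% | 0.9^5 = 0.590 |
| 20% | 0.8^5 = 0.328 |
| 30% | 0.7^5 = 0.168 |

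An event affecting one patient in five would be missed altogether in about a third of such studies.

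**3. What five patients can show about completion.** Exact (Clopper-Pearson) 95% limits for x of 5 are the 0.025 quantile of Beta(x, 6 − x) and the 0.975 quantile of Beta(x + 1, 5 − x). For x = 5 the lower limit is 0.025^(1/5) and the upper limit is 1.

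| Completed | Exact 95% interval |
|---|---|
| 5 of 5 | 48% to 100% |
| 4 of 5 | 28% to 99.5% |
| 3 of 5 | 15% to 95% |

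Even the best possible result leaves a completion rate near one half open.

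**4. Does any planned summary measure feasibility?** Setting the sections side by side:

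- *Study Endpoints:* six physiological measures. None records completion or tolerance.
- *Statistical Analysis Plan:* feasibility is judged from changes in those measures, and the list of what will be reported contains only them.
- *Adverse Events, with the adverse-events row of the Schedule of Assessments:* intolerance is captured at every occasion, but as a safety item.
- *Data Safety Monitoring Plan:* intolerance is documented, with no link to a summary.
- *Schedule of Assessments:* no item for completion or for the time of and reason for early removal. A reading in the column headed "15 mins after PEEP therapy" does not prove the device was still in use, because vital signs can be taken after removal and the plan does not say whether scheduled readings continue in that case.

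The data on intolerance will therefore exist. What is missing is a commitment to summarise them, their use for feasibility, and an explicit record of completion or early removal.

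**The case against.** The strongest reply is that this is one loose sentence in a plan that qualifies itself repeatedly. The SAP directly before it admits low power, no test is planned, and no decision rule or analysis depends on the wording. That is right, and it keeps the point minor. It does not remove it, because this is the sentence that says what the sample will establish.

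On feasibility, the reply is that intolerance is already scheduled at all five occasions and documented one-on-one, and that the SAP reports every measure for every patient at each occasion. With five patients, a session stopped early would often show as a gap. This largely stands. A reader might infer that the protocol fails to capture tolerance; it does capture it. The gap lies in the SAP's summary and in the missing completion item. A gap in the readings is also not a reliable sign of removal, as shown above.

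Intolerance itself has no criterion or time limit in the adverse-event list, so the limits above illustrate any event judged yes or no. They are not a precise statement about that item, nor about listed events that have no threshold.

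A reader might also want the Study Objective changed, since it says: "The objective of this study is to determine the safety, feasibility and efficacy". That is ordinary wording for an objective. It makes no claim that five patients suffice, so it can stand.

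**Conclusion.** The point holds and is minor. The sufficiency sentence is not supported by the design and conflicts with the plan's own framing: no events in five leaves a true rate of up to 52% open (45% one-sided), and full completion leaves anything from 48% upward open. These figures rest on an assumed 95% level and on outcomes decided yes or no for each patient. The SAP's rule for feasibility uses endpoints that do not measure it.

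A reader might infer that five patients is the wrong number. The documents do not support that: this is a descriptive pilot with no planned inference, and more patients would not cure the feasibility measure. Nor is there a fault in safety monitoring here. The effect is confined to what the trial may conclude and report.

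**What to change.** 1. **Sample Size and Accrual.** Replace the sufficiency sentence with: *Five patients will provide a preliminary description of safety, feasibility and change in oxygenation, to determine whether further investigation is warranted; 0 of 5 patients with a given event would still be compatible with a true rate of up to 52% (exact two-sided 95% limit).*

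2. **Statistical Analysis Plan.** Assess feasibility by the number of patients who complete the 15 minutes, out of those enrolled. List separately any patient who is enrolled but never starts the device, since enrolment comes before the mouthpiece is delivered. Report early removals by reason, counting removal for clinical decline separately from inability to tolerate the mouthpiece, because the first is a safety matter and the second a feasibility matter. An exact 95% interval may be added but is not essential.

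3. **Schedule of Assessments.** Add one item: completion or early removal, with time and reason. The investigator already watches the session and can record it then.

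No change to the objective or the sample size is needed. The cost is a less favourable stated claim and one extra recorded item, with no added patients, visits or procedures.

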## **General Design Limitations**

Possible pitfalls may include the variable course of COVID-19 infection that may affect the results of the analysis and the unknown nature and progression of this disease.

## **Protection of Human Subjects**

### *Institutional Review Board (IRB) Review and Informed Consent*

Screening and enrollment will not begin until the Emory University IRB has approved the study protocol and informed consent form.

A physician investigator or study team designee(s) will obtain the informed consent via HIPPA compliant communication technology. A physician-investigator or study team member designee(s) will begin the verbal informed consent process with the subject with a diagnosis of COVID-19 infection. The nature of this infection precludes the research team from obtaining written consent before admission or in-person once the patient is admitted due to possible COVID-19 exposure and the handling of contaminated documents/pens. According to Emory critical care physicians, research staff are not permitted to enter COVID + rooms.

All COVID-19 positive patients will be screened for potential participation in the study. For the patients located in a telemetry unit or medical floor, a member of the research team will contact the patient remotely via phone (landline or via HIPAA compliant telehealth) to obtain verbal consent and give instruction on use of the device. Should the patient already be located in the ICU, and is unable to use the phone, the investigator will obtain consent via eICU. The patient must verbalize understanding of the consent before he/she consents. The subject's verbal consent will be obtained before any research related procedures are performed.

Once the patient meets inclusion criteria and is enrolled in the study, the investigator is responsible for getting the mouthpiece to the patient via healthcare staff. During the actual 15 minutes that the patient is using the GO2 PEEP MOUTHPIECE, the investigator will be able to monitor and communicate with the patient via eICU. The patient will also be able to communicate/view the investigator as well. The investigator will be able to collect all data remotely during this period.

### *Subject Confidentiality*

Subject confidentiality will be guaranteed by storing all data collected in a password-protected database with no associated PHI or patient identifier information included. Patients in this database will only be identified via a unique study ID number. This study ID number will link the electronic data set of each patient to their PHI that will be stored separately in the research study binder.

### *Subject Safety*

Subject safety is of utmost importance throughout this study. If at any time there is a worsening of the patient's condition, the GO-2 PEEP MOUTHPIECE will be immediately removed and standard therapy will be directed by the critical care medicine team.

#### *Adverse Events*

Patients will be assessed for the following adverse events:

- Decreased oxygen saturation
- Increased respiratory rate
- Increased heart rate
- Low blood pressure
- Increased work of breathing
- Worsening arterial blood gases (if available)
- Patient unable to tolerate the mouthpiece

All serious adverse events will be assessed and reported per the Emory IRB Policies and Procedures.

#### **Data Collection**

Study data will be collected from the patient's electronic medical records. All information will be entered in a de-identified fashion into a password protected Microsoft Excel spreadsheet created for the study. All study data will be coded using indirect identifiers consisting of a unique numeric study ID code linked to each study participant's name to enable verification of study data against source data, as needed.

Study data, including Protected Health Information (PHI), will be obtained with the patient's direct authorization through the consent form in accordance with HIPAA policy. PHI will be obtained via patient medical records as noted above. Permission for use or evaluation of PHI will be limited to the principal investigator, and research study staff. The PHI will be a part of the clinic record and patient study binder. The binders will be kept in a secure location when not being used by the research staff. The PHI collected will be used by the PI and research staff for study tracking purposes, to link and confirm study data with the information located in the patient's clinical record, and if patient safety necessitates, to communicate relevant findings with the patient's healthcare providers. The PHI will be destroyed using the institution's official recycling system once the study is completed. The PI and staff will maintain the records of the study including all correspondence, the study protocol with any/all amendments, all correspondence with and approval from the Emory IRB, and signed informed consent forms in the Regulatory Binder. All these materials, along with individual patient files, data collection forms and source data will be stored and maintained, along with a record of the location of storage, for up to 6 years after the completion of the study. Records will be destroyed using the official institutional recycling system.

## **Data Management**

Upon study completion the final data set will be provided to Sponsor and stored within the secure server in the Houston Plastic Craniofacial and Sinus Surgery office ([name]). All non-identifiable patient data collected will be stored on a password encrypted Microsoft Excel document on the same server. No information will be transmitted electronically outside of the server nor will any data be stored off of the server on any portable type media storage device. All study participant PHI and personal contact information will be securely stored on an encrypted, password-protected drive or device or in a study binder at Emory Saint Joseph's research office.

## **Data Safety Monitoring Plan**

With this very small, single-center, open label trial, there will not be a DSMB. However, the Principal Investigator will personally monitor each patient's use of the device. Therefore, there will be one-on-one physician monitoring, assessment and documentation for adverse effects and intolerance of device usage. If the subject experiences an adverse event as a result of the device, and the investigator staff believe it is in the best interest to discontinue study participation, the patient will be withdrawn. Any unanticipated or unforeseen complications will be reported by the investigator (or authorized designee) to the IRB.

## **Facilities**

The study will take place at Emory University Hospital, The Emory Clinic and Emory Saint Joseph's Hospital.

## **Funding Source**

There will not be funding for this study. GO-2 PEEP MOUTHPIECEs will be provided at no cost by PEEP Medical, LLC.

### **GO2 PEEP MOUTHPIECE**

1a – PEEP Mouthpiece valve closed during expiration.

1b – PEEP Mouthpiece valve open during inhalation.

